PI name: [name]
Protocol number: 15-M-0151
Version: Am C

Protocol Title: An Investigation of the Antidepressant Effects of the Glycine Receptor Antagonist AV-101 (4-chlorokynurenine) in Major Depressive Disorder

Abbreviated Title: Antidepressant effect of AV101

Protocol Number: 15-M-0151

1. Précis

a. Objective

Modulation of the NMDA receptor (NMDAR) complex or other components of glutamatergic signaling is likely involved in improvement of depressive symptoms and related constructs/dimensions of observable behavior and neurobiological measures. Current standard monoaminergic pharmacological approaches for major depressive disorder (MDD) have proven to be only modestly effective during acute depressive episodes. We have systematically tested different glutamatergic modulators in patients with mood disorders in order to develop improved therapeutics. We found that the NMDAR antagonist ketamine produces rapid antidepressant effects in patients with treatment-resistant depression (in MDD and Bipolar Disorder). However, despite being highly efficacious, the proof of concept ketamine produces psychotomimetic effects.

In the present protocol, we aim to evaluate a new glutamate-mediated mechanism associated with antidepressant efficacy by targeting the glycine receptor within the NMDA receptor. Targeting the glycine coagonist site of the (NMDA) receptor may bypass potential adverse effects that occur with ketamine without affecting the robust efficacy observed. This may then result in the "glutamate surge" that has been associated with the rapid acting antidepressant effects of ketamine.

The present Phase 2 proof-of-concept study is designed to evaluate the antidepressant effects of AV-101 (*L-4-chlorokynurenine or 4-Cl- KYN*) in MDD; this is a synthetic compound which is enzymatically converted into the selective glycine/NMDAR antagonist 7-chlorokynurine (7-Cl-KYNA) after crossing the blood brain barrier (BBB) and then reaching brain glial cells. In animal models of depression, 4-Cl-KYNA (AV-101) induced acute and prolonged antidepressant-like effects without exhibiting ketamine-like side effects as determined by the drug discrimination, conditioned place preference, and pre-pulse inhibition tests.

We will also evaluate the neurobiological mechanisms involved in the antidepressant response to AV-101. We expect that this effect may modulate glutamate transmission and reverse the clinical symptoms of depression. The demonstration that a glycine-antagonist produces antidepressant effects without psychotomimetic side effects would support the therapeutic relevance of the glycine site of the NMDAR and could direct the development of novel drug targets for the treatment of depression.

b. Design

Male and female patients, ages 18 to 65 years, with a diagnosis of MDD, currently in an episode of major depression, will be recruited for this study. This study will consist of a randomized, double-blind crossover administration of either the glycine receptor antagonist AV-101 (1,080 or 1,440 mg/day given orally) or placebo for 2 weeks. The study will assess the efficacy in improving overall depressive symptomatology and tolerability of AV-101 in treatment-resistant MDD. Other aims of the study include: 1) determining whether changes in brain neurochemicals (e.g. glutamate) and peripheral biomarkers obtained via MRS and cerebrospinal fluid (CSF) correlate with antidepressant response (decrease in Hamilton Depression Rating Scale (HDRS) total scores) to AV-101 in patients with treatment-resistant MDD, and 2) examine other potential biomarkers of response.

c. Outcome Measures

Primary: Hamilton Rating Scale (HDRS) total score.

PI name: [name]
Protocol number: 15-M-0151

Version: Am C

Secondary: Proportion of subjects achieving remission (HDRS \leq 7) and response (\geq 50% reduction from baseline in HDRS total score); change from baseline in Hamilton Anxiety Rating Scale (HAM-A), Montgomery-Asberg Depression Rating Scale (MADRS), and the Columbia Suicide Severity Rating Scale (C-SSRS) total scores. Surrogate biomarkers of drug effect/response include: changes in prefrontal glutamate levels measured with 7T 1 H-MRS.

PI name: [name]
Protocol number: 15-M-0151

Date: 05-15-18
Version: Am C

2. STATISTICAL ANALYSIS

a. Analysis of data/study outcomes

The double blind will be broken and the randomization status of each participant will be revealed only after the completion of this study in all 20 individuals. An interim **blinded** analysis may be performed no more than one time (for example, at the request of the PI's Board of Scientific Counsellors) to inform ongoing scientific efforts and productivity of the Branch; however, this interim analysis will not serve as the basis for decisions to change study procedures or to terminate the study. (**Specific Aim 1**) To assess the efficacy of AV-101 compared with placebo in improving overall depressive symptomatology over a two-week course of treatment in patients with treatment-resistant MDD currently experiencing a major depressive episode.

The primary aim will be accomplished by assessing the efficacy of two weeks of oral AV-101 (1,080 or 1,440 mg/day) compared with placebo in improving overall depressive symptomatology. The primary assessment of efficacy is a comparison of HDRS scores between treatment groups.

The difference between AV-101 and placebo will be examined using a linear mixed model with restricted maximum likelihood estimation where drug and time are within subjects factors. Drug and time main effects and their interaction will be included in the model as within subjects factors. Baseline scores for each phase will be used as a time-dependent covariate. A random intercept and subject effect will be included if they contribute significantly to the model. Schwarz's Bayesian criteria will be used to examine the most appropriate covariance structure prior to formal analyses, where a compound symmetry structure will be used in another is not preferred. Bonferroni corrected post hoc tests will be used to follow up on a significant drug by time interaction. Cohen's d will be calculated to describe the effect size.

Additional follow-up analyses may examine the potential for carryover effects within the crossover study. First, an additional phase variable may be added to the original statistical model. Second, results in the first phase of the study may be examined separately to understand whether any drug effect remains in a parallel-like design.

Secondary analyses will be conducted in the same manner for BPRS, CADSS, C-SSRS, HAM-A, MADRS, PANAS, SHAPS, SSI, TEPS, and YMRS. A similar statistical model will be used to examine secondary measures. Bonferroni-like corrections will be used to determine the significance of secondary analyses.

Criteria for significance

Significance will be evaluated at p<.05, two-tailed.

Analyses will be based on the intent-to-treat (ITT) principle where all randomized subjects who receive baseline and at least one post-baseline assessment will be included. A subject will be considered a responder if the HDRS total score has decreased by 50% or more from baseline to endpoint. Response rates will be analyzed using McNemar's test for repeated measures categorical outcomes.

Safety and tolerability assessments will be based on the safety analysis set which will include all randomized subjects who are given study treatment.

The incidence rate of adverse events will be tabulated by preferred term and system organ class; serious adverse events, adverse events leading to death, and adverse events leading to withdrawal of subjects will be tabulated for each treatment group.

Analyses of surrogate neurobiological markers

Multiple logistic regression models (for categorical outcome, response vs. non-response) will evaluate candidate biological markers for independent association with outcomes. For these models, we will compute robust standard errors or associated 95% confidence intervals.

PI name: [name]
Protocol number: 15-M-0151

Date: 05-15-18
Version:Am C

b. Power analysis

Previous studies by our group (see **Background**) demonstrated improvement in depression at 72 hours with an effect size of d=0.67. Assuming α =.05, two-tailed, 20 patients with MDD would provide 81% power to detect an effect of the same size as previously reported with a double-blind crossover study. We are primarily interested in detecting drugs with a large effect size that occurs within a short period of time (\leq 72 hs) as there are already many antidepressants with small effect sizes after 2 weeks of treatment. This is the reason for not studying a much larger number of patients; in addition, the current study design uses a crossover design.

c. Accrual number

If we assume that 20% of subjects will either not complete the drug free period or will drop out during the crossover double-blind portion of the study, then 25 MDD patients need to be recruited.

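### The plan lets a significance test decide whether the patient effect stays in the primary crossover model; depending on an unstated covariance block, this could unpair the comparison on which the 81% power rests.

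*Combined protocol and SAP*

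**What the plan says.** The Précis (1.b, Design) describes a crossover: "This study will consist of a randomized, double-blind crossover administration". Each patient therefore contributes both AV-101 and placebo scores.

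Section 2.a analyses HDRS with a mixed model fitted by REML. On the fixed part: "Drug and time main effects and their interaction will be included in the model as within subjects factors". On baseline: "Baseline scores for each phase will be used as a time-dependent covariate". On the patient term: "A random intercept and subject effect will be included if they contribute significantly to the model". No test or threshold is named for that last step.

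The next sentence selects the covariance structure by Schwarz's criterion, with a default: "where a compound symmetry structure will be used in another is not preferred" (reading 'in' as 'if'). It does not say whether the structure applies to all of a patient's readings or separately within each phase.

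Section 2.b gives the power: "Assuming α =.05, two-tailed, 20 patients with MDD would provide 81% power to detect an effect of the same size". The effect size comes from earlier work that "demonstrated improvement in depression at 72 hours with an effect size of d=0.67".

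**The concern.** The link between a patient's AV-101 and placebo scores is a feature of the design. It is not a hypothesis for the data to confirm. With 20 patients, a non-significant variance component is poor evidence that the component is zero.

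If the patient effect is the only term joining the two phases, dropping it compares them as though they came from different patients. When the phases are positively correlated, the standard error of the drug contrast is then too large and the test loses power. Section 2.b counts on a paired comparison that section 2.a does not secure. Two analysts following section 2.a in good faith could also fit different primary models and report different p-values.

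**Working it through.** **Inputs from the documents.** n = 20, d = 0.67, two-sided alpha 0.05, stated power 81% (section 2.b); patient effect conditional on significance, compound symmetry as default (section 2.a).

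**Assumed, because the documents do not give them.** The between-phase correlation rho (range 0 to 0.8), the pre-test, and the covariance block.

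**Step 1: reproduce the 81%.** Paired t-test, noncentral t with 19 df and noncentrality 0.67 × √20 = 3.00: power 81.1%. An unpaired t-test with 20 per arm gives 54.2%, and with 10 per arm 29.5%. The stated figure is therefore that of a paired test, with d the standardised within-patient difference.

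**Step 2: what unpairing does to the standard error.** Give each phase value variance 1.
- Paired: SE = √(2(1 − rho)/20).
- Unpaired: SE = √(2/20) = 0.316.
- Ratio, unpaired to paired: 1/√(1 − rho), which is 1.20 at rho 0.3, 1.29 at 0.4 and 1.41 at 0.5.

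**Step 3: the pre-test rule when nothing else carries the pairing.** Trials were simulated on phase means, which is exact for balanced data with compound symmetry within phase. The true difference is 0.67 × √(2(1 − rho)), so the paired test has 81% power at every rho. Let B be half the variance of the patient sums and W half the variance of the patient differences. The estimated patient variance is (B − W)/2.
- Likelihood-ratio pre-test: 19 × [2 ln((B + W)/2) − ln B − ln W] if B > W, otherwise 0, tested at 5% with the boundary correction.
- Wald pre-test: the estimate divided by √(2B²/19 + 2W²/19)/2, compared with 1.96.
- If the effect is kept, paired t (19 df); if dropped, pooled-variance t (38 df).

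| rho | Always unpaired: power | LR: dropped | LR: overall power | Wald: dropped | Wald: overall power |
|---|---|---|---|---|---|
| 0 | 83% | 95% | 84% | 99% | 83% |
| 0.1 | 80% | 89% | 82% | 97% | 81% |
| 0.2 | 77% | 78% | 80% | 93% | 78% |
| 0.3 | 72% | 62% | 78.5% | 85% | 75.0% |
| 0.4 | 65% | 43% | 78.2% | 71% | 73.1% |
| 0.5 | 56% | 24% | 78.8% | 51% | 73.1% |
| 0.6 | 44% | 9% | 80% | 27% | 76% |
| 0.8 | 11% | under 1% | 81% | 1% | 81% |

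A likelihood-ratio test without the boundary correction falls between the two, at about 77% for rho 0.3 to 0.5. Overall type I error at rho 0.3 to 0.5 is 4.3-4.7% (boundary likelihood ratio) and 3.3-3.9% (Wald).

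**Step 4: compound symmetry across both phases, with no random intercept.** With one value per phase in a simulated data set, the standard error of the drug effect equals the paired one: 0.298 at rho 0.3 and 0.238 at rho 0.5, against 0.316 and 0.321 under independence. With four readings per phase it stays nearer the paired value than the independence value: 0.140 against 0.138 paired and 0.162 independent at rho 0.3; 0.114 against 0.097 and 0.174 at rho 0.5. Pairing is kept, and a random intercept would duplicate a parameter already in the model.

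**Limits.** The simulation has no period effect and no missing data. Adjusting for each phase's baseline may lower the residual rho.

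**The case against.** The strongest reply is that section 2.a treats drug and time as varying within patient and then adds compound symmetry by default. The usual block for such a model is the patient, across both phases, and on that reading Step 4 shows that dropping the random intercept changes nothing. This stands as a plausible reading. It is not a guarantee: the block is not stated, and compound symmetry gives way if Schwarz's criterion prefers another structure, which might carry little between-phase correlation.

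A second reply concerns order. Section 2.a mentions the intercept before the covariance structure. If the intercept is tested against independent residuals, the test is much stronger. With between-phase correlation 0.3 to 0.5, an assumed within-phase correlation of 0.5 to 0.7 and 3 to 5 readings per phase, the likelihood-ratio test keeps the patient effect in 97-100% of simulated trials. The Wald test keeps it in 77-99% with 3 readings and 91-100% with 4 or 5. This also stands. The plan fixes neither the order nor the test, so the drop rates in the table are conditional.

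Third, a reader might infer that the rule must be either harmful (within-phase block) or empty (compound symmetry across phases). That is not exhaustive. With, say, an autoregressive structure over the whole patient, a random intercept is a separate, testable term, and adding it when supported is ordinary model building.

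None of this defends testing a term that the design already justifies.

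**Conclusion.** The rule is poor practice and should change, but the documents do not show that it reduces power. A reader might infer that power falls below 81% as a matter of course. That needs three things the plan does not state: a covariance block confined to one phase (or a chosen structure with little or no between-phase correlation), a mid-range correlation, and a pre-test that often fails to reach significance. Granting all three, power at rho 0.3 to 0.5 is about 78-79% (boundary likelihood ratio) or 73-75% (Wald) instead of 81%. There is little or no loss near rho 0-0.1 or 0.8, and none from this rule if compound symmetry spans both phases.

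A reader might also infer a serious distortion of the error rate, because among trials where the effect is dropped the false-positive rate is only 1-2%. That figure is conditional on the drop. Overall type I error is about 3-5%, slightly conservative and not inflated.

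The point is a cheap improvement to the primary model, not a demonstrated shortfall in power.

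**What to change.** In section 2.a, replace the sentence on the random intercept with: *Patient is included in the primary model whatever its significance, because treatment is randomised within patient; no test is used to remove it.*

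Then state the covariance block, in one of two forms:
- a random patient effect, with the structure chosen by Schwarz's criterion applied to readings within a phase; or
- a structure across both phases of a patient that allows correlation between phases, with no separate random intercept where it would duplicate a parameter.

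Settle this before unblinding, and carry it to the secondary scales, which section 2.a analyses with a similar model.

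The cost is a sentence or two in the SAP and no extra data. If patient variance is truly zero, always pairing uses 19 error degrees of freedom instead of 38 and gives up about 2 points of power (83% to 81%).

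### The primary mixed model has no subject-by-phase error term, so the drug main effect can be tested against too small an error

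*Combined protocol and SAP*

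**What the plan says.** The primary analysis is in section 2.a (Analysis of data/study outcomes) of the combined protocol and SAP. It is a REML linear mixed model for HDRS.

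- Fixed effects: "Drug and time main effects and their interaction will be included in the model as within subjects factors".
- Covariate: "Baseline scores for each phase will be used as a time-dependent covariate".
- Random effects: "A random intercept and subject effect will be included if they contribute significantly to the model". No subject-by-phase or subject-by-drug effect is named.
- Covariance: chosen by Schwarz's criterion, "where a compound symmetry structure will be used in another is not preferred" (the word *in* is evidently a slip for *if*).
- Phase: an optional carryover check only, "First, an additional phase variable may be added to the original statistical model".

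The section does not say whether the covariance block is the whole patient or one phase of a patient. It does not list the structures to be compared, and it names no degrees-of-freedom method. Tests are two-sided at 5%. The analysis set keeps patients with partial data, "where all randomized subjects who receive baseline and at least one post-baseline assessment will be included".

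**The concern.** A patient is on one treatment for the whole of a phase. The drug main effect is therefore a contrast between two phase means per patient, and its error must carry whatever makes one phase of a patient differ from the other. Extra visits within a phase do not average that component away.

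Drug and time are both called within-subject factors, which suggests one covariance block per patient. Compound symmetry on that block treats two visits in the same phase as no more alike than two visits in different phases. If they are in fact more alike, the standard error of the drug main effect is too small, and the shortfall grows with the number of visits.

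The plan's own covariate adds to this. Measurement noise in a phase baseline, multiplied by its slope, is shared by every visit of that phase.

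At stake is the main test of Specific Aim 1. With no true effect it could reach p<.05 in more than 5% of trials, with a confidence interval that is too narrow. The same modelling approach is carried over to the secondary scales.

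**Working it through.** **Inputs from the documents.** 20 patients in a two-phase crossover; two-sided 5% level; d = 0.67 and 81% power (section 2.b); 20% loss and 25 recruited (section 2.c).

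**Assumptions, because the documents do not give them.** K = 2, 4 or 6 post-baseline visits per phase. Variances subject/phase/residual of 0.5/0/0.5, 0.5/0.1/0.4, 0.4/0.2/0.4 and 0.4/0.3/0.3. The baseline either carries the phase effect or does not.

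**1. The plan's own figures.** The effect comes from earlier work that "demonstrated improvement in depression at 72 hours with an effect size of d=0.67". For a paired t-test, the noncentrality is 0.67 × √20 = 2.996 on 19 df (critical value 2.093), which gives power 0.811. Accrual is 20/0.8 = 25. Both reproduce. The sizing thus assumes one within-patient difference per patient.

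**2. Closed-form check, without the covariate.** Let τ² be the subject-by-phase variance and σ² the residual variance.

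- True variance of a patient's phase-mean difference: (2/K)(σ² + Kτ²).
- Patient-wide compound symmetry pools 2K−1 within-patient contrasts, of which only one is the phase contrast. It therefore uses (2/K)(σ² + Kτ²/(2K−1)).
- Ratio of true to assumed variance: R = (σ² + Kτ²)/(σ² + Kτ²/(2K−1)).
- False-positive rate ≈ 2[1 − Φ(t/√R)], with t the 97.5% point on 19(2K−1) df.

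| K | τ²=0.1, σ²=0.4 | τ²=0.3, σ²=0.3 |
|---|---|---|
| 2 | R = 0.600/0.467 = 1.29, about 8% | R = 0.900/0.500 = 1.80, about 14% |
| 4 | R = 0.800/0.457 = 1.75, about 13% | R = 1.500/0.471 = 3.18, about 27% |
| 6 | R = 1.000/0.455 = 2.20, about 18% | R = 2.100/0.464 = 4.53, about 35% |

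REML simulation with compound symmetry forced and the baseline covariate included gives 8.5-15.3%, 12.5-30.5% and 18.3-39.4% at 2, 4 and 6 visits, in line with this.

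**3. With Schwarz's criterion choosing.** Null trials, 1,000 in each of 50 settings, REML, drug × time plus phase baseline, Satterthwaite df, Monte Carlo SE 0.7-1.5 points. Data were complete (20 patients) or had 5 of 25 randomised patients dropping out at a random visit, unrelated to outcome. False positives for the drug main effect with phase variance 0.1-0.3:

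| Candidates on a patient-wide block | Rate |
|---|---|
| Compound symmetry, AR(1), subject + AR(1) | 7.5-12.3% (K=2), 10.4-17.1% (K=4), 16.2-25.2% (K=6) |
| The same plus drug-by-time direct products | 3.9-12.8% |
| The same three plus subject-by-phase | 4.6-10.0% |

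The criterion does not reliably repair the error term at this sample size. It keeps compound symmetry in 67-79% of trials at phase variance 0.1 with 4-6 visits, and in 5-37% at 0.3. In separate runs (K=4, no covariate) with a subject-by-phase structure offered, it still chose plain compound symmetry in 262 of 300 trials when phase made up 0.1 of the within-patient variance, and in 87 of 300 at 0.3.

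**4. The covariate alone.** With no phase variance the rates are 6.6-8.1% across these lists, against 5.0-5.1% under compound symmetry without the covariate. This part is less secure. Other REML runs under compound symmetry gave 5.5-8.4%, but one further set of simulations showed no inflation (4.8-5.2%).

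**5. What is not exposed.** First-visit contrast, Schwarz-selected: 4.5-9.5%. Drug-by-time test under compound symmetry: 0.5-3.6%, so conservative.

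**6. Period, a separate and smaller point.** With a 0.5 SD period shift, 4 visits, no phase variance and the three-structure list, omitting period gives 8.0% at 10/10 sequences (7.5% with no shift) but 12.9% at 12/8. The harm comes with unequal sequences.

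**7. The proposed model.** 3.5-7.0% over all 50 settings; a phase-mean crossover with period gives 3.2-6.3%.

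**The case against.** The strongest reply is that the block may be the patient-phase. On one patient-wide block, compound symmetry and a positive subject intercept describe the same covariance, so planning both would be redundant. They are distinct only if compound symmetry applies within a phase, and a subject intercept plus within-phase compound symmetry is the core of the proposed fix. This is a fair reading, and under it there is no inflation. The text does not settle it, however, because the random effects stay only if significant. If the subject effect is dropped under that reading, the test errs the other way: 2.0-4.8% in one set of assumptions, and 0.1-0.2% in another (phase 0.3 of the within-patient variance, subject variance equal to it). The same fix cures both directions.

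Second, the highest rates depend on assumed visit counts and on a candidate list the plan does not contain. That stands, and it is why the result is a range. Some inflation remains on the wider lists.

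Third, section 2.c counts losses in the drug-free period as well ("If we assume that 20% of subjects will either not complete the drug free period or will drop out"), so putting all 5 losses after randomisation overstates dropout. That is correct but of little consequence: on the three-structure list the complete-data range is 8.1-23.8%, against 7.5-25.2% with dropout.

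Fourth, the proposed model's own range (3.5-7.0%) overlaps the 6.6-8.1% attributed to the covariate alone, and the plan gives no power for the drug main effect, so the power cost of a wider standard error cannot be read from it. Both points stand. The case rests mainly on phase variance above zero.

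**Conclusion.** The concern holds. As written, the named default and the selection rule allow the drug main effect to be tested against an error that omits between-phase variation within a patient. For 2-6 visits per phase and phase variance of 0.1-0.3 of the total, the false-positive rate is 7.5-25.2% if no candidate structure represents phase, and up to 10.0% (subject-by-phase) or 12.8% (direct products) if one does. The 18-39% figures at 6 visits require compound symmetry to be kept throughout, which the plan does not say.

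The result rests on a patient-wide block and on assumed visit counts and variances. Outcome-related dropout was not simulated. It concerns the drug main effect: single-visit contrasts are affected much less, and the drug-by-time test is conservative under compound symmetry. It should be fixed, because it bears on the primary test and the remedy is cheap. Confidence is medium, because the inputs that set the size are not in the documents.

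**What to change.** Replace the random-effect and covariance sentences in section 2.a with:

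> Random effects for subject and subject-by-phase, and a fixed effect for period, will be included in the primary model regardless of significance. Schwarz's criterion will choose only the residual covariance within a patient-phase, from independent, heterogeneous-variance and, with three or more visits per phase, AR(1) structures. Kenward-Roger degrees of freedom will be used.

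AR(1) is left out at two visits because it cannot then be told apart from the subject-by-phase effect. A simpler alternative is to analyse each patient's mean post-baseline HDRS per phase as a two-period crossover with a period term; time-specific contrasts would then need their own analysis.

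The cost is SAP wording and a wider standard error for the drug main effect. With no phase variance it is 1.11-1.20 times the compound-symmetry one and 1.07-1.19 times the Schwarz-selected one. With phase variance 0.1-0.3 it is 1.10-1.61 times the Schwarz-selected one, and there much of the difference is variation the narrower standard error leaves out. The stated sizing needs no change, since 81.1% is the power of a paired test on one difference per patient.

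### The primary crossover model has no phase term; phase is offered only as an optional carryover check, which a phase main effect cannot provide

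*Combined protocol and SAP*

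**What the plan says.** The précis describes a randomized, double-blind crossover of AV-101 and placebo. Section 2.a sets out the primary HDRS model: "Drug and time main effects and their interaction will be included in the model as within subjects factors". It adds one covariate: "Baseline scores for each phase will be used as a time-dependent covariate". Neither phase nor sequence is listed.

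Phase comes up in the next paragraph, among optional analyses of carryover: "First, an additional phase variable may be added to the original statistical model". Time in the primary model therefore cannot mean phase. No sequence or drug-by-phase term is named. The other optional check is that "results in the first phase of the study may be examined separately to understand whether any drug effect remains".

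The same approach extends to ten further scales: "A similar statistical model will be used to examine secondary measures". For the analysis set, "all randomized subjects who receive baseline and at least one post-baseline assessment will be included". Section 2.c allows for 20% losses, in the drug-free period or during the crossover, and so recruits 25 patients to obtain 20. The text gives no allocation method and no expected period effect.

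**The concern.** The phase term has been given the wrong job, and its right job has been left optional.

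- **Wrong job.** A phase main effect estimates how scores in phase 2 differ from those in phase 1, averaged over sequences. Carryover from AV-101 into the following placebo phase shows up as a sequence (drug-by-phase) difference. A quiet phase term could be read as evidence against carryover, and a large one as evidence for it. Neither reading is sound.
- **Right job left optional.** If depression scores differ between phases for any reason, a model without phase puts that difference into the error term when sequences are balanced. When they are not, part of it goes into the drug estimate. Leaving phase to discretion also allows two primary estimates, with the choice open after unblinding.

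**Working it through.** **Inputs.** From section 2.b: d = 0.67, N = 20, two-sided α = 0.05, stated power 81%. From section 2.c: 25 recruited. Assumed: period shift π and carryover λ, both in SD of the within-patient difference (set to 1), and between-phase correlation ρ from 0.3 to 0.7. One post-baseline value per phase is used throughout.

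**1. The plan's figure.** Paired t-test, noncentrality 0.67 × √20 = 3.00. With 19 df, power is 81.1%, which matches the plan. With phase added (18 df) it is 80.9%.

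**2. What the phase term estimates.** Let AB mean AV-101 first. The expected change from phase 1 to phase 2 is π + λ − δ in AB and π + δ in BA, where δ is the drug effect. With 10 per sequence:
- Phase coefficient = average of the two = π + λ/2.
- Drug estimate = half of (BA − AB) = δ − λ/2, with or without phase in the model.

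With λ = 0.335 and π = 0, the phase coefficient is 0.17 and the drug estimate 0.67 − 0.1675 = 0.50. A pure period effect of 0.17 gives the same phase coefficient and leaves the drug estimate at 0.67. The phase term cannot separate the two cases. In simulation:
- π = 0.5 without carryover made phase significant in 57% of trials.
- λ = 0.67 with π = −0.335 did so in only 5%, although the drug estimate was biased by −0.335, half the drug effect.

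**3. Power without phase, 10/10, no baseline covariate** (200,000 simulated trials per setting):

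| Shift π | 0 | 0.25 | 0.5 | 0.75 | 1.0 |
|---|---|---|---|---|---|
| Phase omitted | 81% | 79% | 74% | 64% | 51% |
| Phase included | 81% | 81% | 81% | 81% | 81% |

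At π = 0.5 the test without phase has a true type I error of about 3%, so it is conservative.

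**4. Power lost with the planned phase baseline as covariate, 10/10** (random-intercept REML, 18 assumed correlation sets, 8,000 trials each; points lost by omitting phase):

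| Shift π | Already in baseline | Arises after baseline |
|---|---|---|
| 0.25 | 0–1 | 1–2 |
| 0.5 | 0–5 (median 1) | 3–8 (median 6) |
| 1.0 | 0–13 (median 3) | 14–32 (median 25) |

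**5. Bias with unequal sequences.** Without phase, bias = π × (n_BA − n_AB)/N. Its size is (11 − 9)/20 = 0.1, (12 − 8)/20 = 0.2 and (13 − 7)/20 = 0.3 times the shift at 11/9, 12/8 and 13/7. The larger sequence sets the sign. If the baseline covariate already carries the shift, bias at 12/8 falls to about 0.05–0.08 times the shift. If 12/8 completers are joined by 1 and 4 patients with phase 1 only, generalized least squares without phase or baseline gives 0.14–0.18 times the shift. With phase in the model the bias is 0. Type I error at π = 0.5 is 4–5% at 12/8 and 6–7% at 13/7.

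**6. Chance of 12/8 or worse among 20.** If 25 are randomized 13/12 and five are lost at random: [C(13,1)·C(12,4) + C(12,5) + C(13,5)] / C(25,5) = (6,435 + 792 + 1,287)/53,130 = 16%. If only three or four losses follow randomization it is 9%; with two or fewer it is 0. Simple randomization of 20 gives 50%.

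**7. Precision of direct looks at carryover, 10 per sequence.** The single-phase SD is σ = 1/√(2(1 − ρ)), which is 0.845 at ρ = 0.3 and 1.291 at ρ = 0.7.
- Phase 1 alone: SE = σ√0.2 = 0.378 to 0.577; power for 0.67 is 39% down to 20%; 95% CI half-width is 2.10 × SE = 0.79 to 1.21.
- Sequence term: SE = √(2σ²(1 + ρ) × 0.2) = 0.609 to 1.065; power is 8% to 6% for λ = 0.335 and 18% to 9% for λ = 0.67.
- Phase-2 baseline compared between sequences, if carryover is fully present there: power is 13% to 8.5% for λ = 0.335 and 39% to 20% for λ = 0.67.

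**The case against.** Several points on the other side have force.

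- **The plan has a baseline covariate.** The 79/74/64/51% series describes a model without it. With it, losses at a shift of 0.5 are a few points. The 14–32 point losses need a shift of 1.0, about 1.5 times the assumed drug effect, and nothing in the document supports a shift that large. This stands, so the adjusted table in step 4 is the better guide.
- **One value per phase is a simplification.** The plan models repeated assessments. A constant phase shift cancels from the drug-by-time contrast, and power for the repeated-measures test may differ considerably. This also stands: the figures are a single-endpoint approximation. It does not make omission safe, because an overall drug effect remains exposed to the shift.
- **Imbalance may be small.** Some of the 20% losses are expected in the drug-free period and may precede randomization. The 16% is therefore a high case under near-equal allocation, and the 50% applies only if randomization was simple. With balance there is no bias.
- **Carryover is not left to the phase term alone.** The phase variable is not defined as a main effect only, and the first-phase comparison is free of carryover. That comparison is optional, however, and too imprecise to show whether a drug effect persists.

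These points limit the size of the harm. They do not give the phase main effect any ability to identify carryover, and they offer no reason to leave phase out.

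**Conclusion.** The concern holds and should be fixed. That a phase main effect neither tests nor removes carryover follows from the design and needs no assumed period effect.

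The harm from omitting phase depends on a period effect the document does not give. For an assumed shift of 0.5 SD of the paired difference, balanced sequences and one endpoint per phase, the loss with the planned baseline covariate is 0–5 points of power if the shift is already in the baseline and 3–8 if it arises later. At 12/8 the bias among completers runs from about 0.05 to 0.2 times the shift. That is 0.025 to 0.10 at a shift of 0.5, against an assumed effect of 0.67. Confidence in these magnitudes is medium.

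**What to change.** Before the unblinding that section 2.a places at study completion, amend the text as follows.

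1. State that phase (1 or 2) is a fixed effect in the primary model, and in the secondary models built on it, in all cases; that it adjusts for period differences; and that it is not a test of carryover.
2. Replace the carryover follow-up with two descriptive results, neither of which decides which analysis is primary: (a) the first-phase AV-101 minus placebo difference in HDRS with a 95% CI, given as an estimate; (b) the between-sequence difference in phase-2 baseline HDRS, and the sequence term if fitted, with 95% CIs.
3. State that these have low power at N = 20 (step 7), so a null result is not evidence that carryover is absent.
4. Report the number of patients analyzed per sequence and phase.

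The cost is wording and one degree of freedom per model, with no new data or visits. If there is no period effect, power goes from 81.1% to 80.9% at 10/10. In the simulations without the baseline covariate it goes from about 81% to 79% at 12/8 and 77% at 13/7.
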